Treg	regulatory T cells
U	unit
ULN	upper limit of normal
UPCI	University of Pittsburgh Cancer Institute

## 1 STUDY OBJECTIVES

### 1.1 Primary Objectives

- To determine the safety of the combination of IV. rintatolimod administered with or without IV IFN $\alpha$  (INTRON® A) in patients with cancer with COVID-19.
- Determine the kinetics of viral load in nasopharyngeal swabs in the course of treatment and Days 7 and 14.

### 1.2 Secondary Objectives

- To assess the efficacy of the treatment combination in patients with cancer with COVID-19.
- Determine the kinetics of viral load in the peripheral blood in the course of treatment and Days 7 and 14.
- Determine the kinetics of changes of the immune subsets and circulating inflammatory mediators (including CRP, cytokines, chemokines, interferons) in peripheral blood in the course of treatment and Days 7 and 14.
- Determine the induction of known mediators of antiviral immunity that include (myxovirus resistance gene, MxA; protein Kinase R (PKR); oligoadenylate synthetase-2 (OAS2); RNase-L, IFN-stimulated gene-15 (ISG15); IFN-induced proteins with tetratricopeptide repeats (IFIT1) and IFN-inducible transmembrane protein 3 (IFITM3), TLR3, RIG-I, MDA5, IRF3, IRF7, in nasopharyngeal swabs material and blood cells of patients on all tiers of treatment. Expression of ACE2 (receptor for SARS-CoV-2 entry) and potentially other genes involved in SARS-CoV-2 infection will be tested in nasopharyngeal samples.

## 2 BACKGROUND

### 2.1 Enhanced Risk of COVID-19 Mortality and Morbidity in Cancer Patients

Patients with cancer and COVID-19 had a 5-fold higher risk of severe events, defined as ICU admission requiring invasive ventilation or death, than those without cancer (1). Currently, there is no proven effective treatment of COVID-19 beyond supportive care. **This trial is based on the central premise that SARS-coronaviruses persist in host cells and in infected hosts by evasion of the innate antiviral responses mediated by RNases (especially RNase-L/OAS) and type-1 interferon (IFN $\alpha/\beta$ ) pathway and IFN-stimulated genes (ISG), and that early therapeutic activation of this pathway will limit viral replication and expansion in patients' tissues, thus preventing severe complications.** SARS-CoV-2 is related to SARS, MERS, and other coronaviruses, which are positive-sense RNA viruses that generate dsRNA during replication. One of the principal IFN antiviral pathways involves activation of the host RNases, especially RNase L, which is induced directly by dsRNA (predominantly by RIG-I and MDA5 helicases (2)) and indirectly by IFN $\alpha/\beta$ , degradation of viral RNA (3) and amplified IFN $\alpha/\beta$  production (2). Coronaviruses avoid upstream pathways that activate type 1 IFNs by cytosolic pattern recognition receptors (e.g. RIG-I and MDA5) preferentially activated by the coronavirus RNA (2, 4), and inhibition or avoidance of IRF3, a transcriptional factor that mediates the induction of type 1 IFNs, by that pathway (5-9). This inhibition of innate immune responses allows the virus to replicate in

Roswell Park Protocol No.: I-659920

host cells, and particularly in high risk patients, progress to pneumonia and respiratory failure. To overcome this barrier to effective immunity, we will evaluate combination rIFN $\alpha$  and rintatolimod. Rintatolimod, a selective dsRNA ligand of TLR3 (but not RIG-I/MDA5 (10)), has strong antiviral activity against multiple viruses, and was found to be protective in a lethal mouse model of SARS-CoV *in vivo*, and show strong anti SARS-CoV activity *in vitro* (11, 12). Combination rIFN $\alpha$  (INTRON® A; 20 MU/M per infusion) and rintatolimod (200 mg per infusion), which showed synergy in activating IFN response signature in preclinical models (10) is being evaluated in clinical trials developed by [name] and colleagues for **patients with multiple solid tumors (active Roswell-held IND-112532 and trials NCT01545141, NCT03403634; NCT03403634), and, in over 70 enrolled patients, has not reached an MTD.**

The rationale for the combination therapy in cancer is based on strong synergy in inducing ISGs and other IFN-regulated genes and promoting type-1 immunity (10); activation of these same pathways is expected to augment antiviral defense in patients with COVID-19. While rintatolimod activates the TLR3/IRF3 pathway to induce IFN $\alpha$ , it does not activate the MAVS/RIGI/MDA5, the alternative RNA-virus-sensing pathway preferentially activated by the coronavirus RNA (2, 4), thus avoiding NF- $\kappa$ B and downstream cytokines (10) that could worsen acute lung injury in COVID-19. We expect INTRON® A to directly enhance the expression of OAS and its ability to promote the RNase L-mediated degradation of viral RNA in virally infected cells that do not mobilize own IFN $\alpha$ / $\beta$  in response to COVID-19, while rintatolimod will induce TLR3-dependent ISGs in the uninfected bystander cells (10), and potentially infected cells, jointly leading to viral degradation. Augmentation of innate immunity in patients with COVID-19 is expected to avert viral progression to respiratory failure and mortality.

These results point to patients with cancer being at a several-fold higher risk for COVID-19-driven morbidity and mortality. Though many treatment modalities are being used, including single agent and combination antiviral agents and immunotherapy, there is no treatment proven to be effective for COVID-19 above supportive care. One promising option was use of HIV protease inhibitors for COVID-19; however, a recent trial showed lack of efficacy (13). Given the lack of effective therapies, there is an urgent need for more effective regimens that could be used prophylactically to prevent COVID-19 (e.g., vaccination) or as upfront therapy; this need is particularly pressing in patients with cancer. In addition, because there is no regimen shown to be more effective than supportive care, we did not include a comparator regimen.

## **2.2 COVID-19: Basic Biology and Rationale for Its Treatment Using the Rintatolimod (Ampligen®) and IFN $\alpha$ Combination**

The COVID-19 is a coronavirus related to SARS, MERS, and other coronaviruses, which use RNA as their genetic material. It spreads in the body and in population by limiting early production of IFN and IFN-related genes, thus avoiding induction of host intracellular RNase L (RNA-degrading enzyme that degrades cytoplasmic host and viral RNA) and activation of innate immunity. There is a large body of literature showing that coronaviruses inhibit upstream pathways that activate type 1 interferons, including inhibition of intracellular signaling driven by pattern recognition receptors (e.g. RIG-I and MDA5) that sense viral RNA and by inhibition of IRF-3, a transcriptional factor that induces the expression of type 1 interferons (5-9). This inhibition of innate immune responses is expected to allow the virus to replicate in epithelial cells, and particularly in high risk patients, progress to pneumonia and respiratory failure. Our goal is to use INTRON® A to directly activate RNase L in virally infected cells with defective ability to

Roswell Park Protocol No.: I-659920

generate endogenous interferon-alpha, while rintatolimod, through ligation of TLR3, will stimulate interferon-alpha expression in bystander uninfected cells, thereby protecting them from viral infection. We also expect the synergy between these two factors in activating IFN-inducible genes, similar to our observations in cancer (10), amplifying the impact of IFN $\alpha$  in infected cells. Seen in this light, augmentation of innate immunity during early mild or moderately severe infection might avert progression to respiratory failure and mortality. In patients with more severe COVID-19, including those with respiratory failure, rintatolimod may promote viral clearance and avert worsening of lung injury. However, augmentation of innate immune responses may also worsen inflammatory lung injury in patients with COVID-19 infection, and therefore safety and efficacy are primary endpoints of this trial. **The current proposal involves repurposing of an investigational immunotherapy regimen developed by [name] for cancer (and currently being evaluated in several clinical trials) to be tested in patients with cancer and COVID-19 disease or significant exposure.**

**Interferon-alpha (INTRON® A) and rintatolimod [Ampligen®]** are two anti-viral drugs and immune activators, currently tested in combination in our ongoing the IRB- and FDA approved clinical trial I 52917 for patients with metastatic colorectal cancer and several other IRB- and FDA-approved trials in other cancers, performed at Roswell and the University of Pittsburgh.

Rintatolimod (selective TLR3 ligand, which activates multiple forms of antiviral immunity) has demonstrated strong antiviral activity against multiple viruses (*see the attached information from AIM*) including the coronavirus SARS COV-1 in vitro and in NIH-contracted animal experiments, conferring 100% protective survival. In vitro activity of Ampligen® against the human coronavirus, OC43, was performed by Barnard, D.L., et al. Proceedings of the 16th International Conference on Antiviral Research, 2003, using BS-C-1 kidney cells (African green monkey). In this in vitro test Ampligen® showed an **EC50 of 0.4  $\mu$ g/ml compared to the easily achievable concentration in humans of 40  $\mu$ g/ml, which is well tolerated**. In in vivo studies (11) and studies at NIH of SARS-COV-1 infected mice (12), Ampligen® conferred conferring a significant antiviral/survival effect.

Since COVID-19 shares key genomic and pathogenic similarities with SARS-COV-1 viruses (*see the attached information from AIM*), it is also expected to be susceptible to rintatolimod.

The second drug, **IFN $\alpha$  has shown antiviral activity** against multiple types of viruses, including other coronaviruses, and is **currently being tested as an anti-COVID-19 agent in multiple countries**.

The **rationale for the combination of these two drugs** in our ongoing clinical trials in cancer and in our proposed trial for COVID-19 patients results from **their strong synergy in inducing IFN-regulated genes and promoting type-1 immunity** (similarly needed for anti-viral and anti-cancer immunity) in human tissues *ex vivo* (10) and the activity of this combination observed in experimental animals (14), as well as the very good safety record of this combination observed in cancer patients so far (*see below*).

## 2.3 Past experience with IFN $\alpha$ and Rintatolimod

**Interferon-alpha** (INTRON® A) is currently FDA approved for the adjuvant treatment of stage III melanoma. It has been examined by multiple investigators as an immune modulator in the setting of vaccine therapy with demonstrated safety (15). It has been extensively evaluated in the setting of metastatic CRC (as single agent or in combination with chemotherapy or IL-2), but was

Roswell Park Protocol No.: I-659920

shown to be largely ineffective (16-33) at daily doses ranging from 3-20 million units/m^2, administered subcutaneously or intravenously. In the treatment of melanoma, a small study by Astsaturov and colleagues (34) administered IFN $\alpha$ -2b in previously vaccinated melanoma patients, and was shown to convert immunization into objective clinical responses, suggesting its ability to amplify the effectiveness of local T cells infiltration and/or function at the tumor site. Vaishampayan et al. examined IFN $\alpha$ -2b 5 million units subcutaneously three times a week following vaccination with a melanoma vaccine (Melaccine) (35). Treatment at this dose was well tolerated. Similarly Mitchell et al. recently completed a large trial examining IFN $\alpha$ -2b, 5 million units subcutaneously three times a week for one year (36). Di Pucchi and Pilla similarly examined the combination of a melanoma peptide vaccine with IFN $\alpha$ -2b, 3 million units subcutaneously three times a week, with little to no toxicity.

We propose to include a short course of high dose interferon alpha-2b (with the dose-escalation lead-in [0-5-10-20] and with maximum 20 million units/m^2, IV, on Days 1 and 3). The maximum dose of 20 million units/m^2 is similar or lower than the previously evaluated doses in melanoma patients (37-39). In this group of patients, in accordance with previous reports, we expect to consistently observe flu-like symptoms. However, this regimen hasn't been evaluated in patients with respiratory viral infection, and additional AEs may be observed. Specifically, augmentation of innate immune responses may also worsen inflammatory lung injury in patients with COVID-19 infection, and therefore safety and efficacy are primary endpoints of this trial.

**Rintatolimod** (Selective toll-like receptor-3 [TLR3] Ligand; analog of poly IC with reduced toxicity for i. v. use).

Rintatolimod (Ampligen®) is a TLR3 specific Poly IC analog in which the cytidylic acid chain has uridylic acid substitutions at a molar ratio of 12:1. Chemokine modulation in temporal association with type I interferon administration is observed with this agent. Rintatolimod has been studied extensively in multiple clinical settings including cancer, chronic viral infection, vaccination protocols, and in chronic treatment of chronic fatigue syndrome.

Rintatolimod has been generally well tolerated with only a low incidence of clinical toxicity. Clinical experience with rintatolimod now totals over 800 patients with more than 200 patients receiving rintatolimod for up to one (1) year, over 50 patients up to two (2) years, and more than 20 patients over two (2) years.

The proposed dosage of 200 mg IV is the starting dose used in chronic treatment of Chronic Fatigue Syndrome (CFS). That dose is escalated to 400 mg IV twice weekly for the CFS indication; however, for use as a chemokine modulator, pharmacologic peak serum levels are achieved at 200 mg; thus, 200 mg daily for 3 days will be incorporated for the immune modulation regimen. Preclinical evidence demonstrates the synergy between IFN $\alpha$  and rintatolimod in inducing the production of the effector T cell-attracting chemokines.

Status: COMPLETED; MANUSCRIPT IN PREPARATION

Phase: Phase IIa (combination with Celecoxib).

- **I 62218 (NCT03403634)** Chemokine Modulation Therapy and Pembrolizumab in Treating Participants with Metastatic Triple-Negative Breast Cancer. ([name] and [name])

Status: CLOSED TO ACCRUAL

Phase: Phase IIa (combination with Celecoxib and Pembrolizumab).

- **I 73718** Phase I Clinical Trial Assessing the Combination of Chemokine Modulation with Neoadjuvant Chemotherapy in Triple Negative Breast Cancer **IND 145344**. ([name] and [name])

Status: COMPLETED; MANUSCRIPT IN PREPARATION

Phase: Phase I (combination with Celecoxib and Paclitaxel).

- **I 77318 (NCT03899987)** Aspirin and rintatolimod With or Without Interferon-alpha 2b in Treating Patients with Prostate Cancer Before Surgery" ([name] and [name])

Status: FDA (IND 143104) and IRB approved. ACCRUING PATIENTS

Roswell Park Protocol No.: I-659920

## **2.5 Rationale for eliminating celecoxib from the proposed regimen and for reducing, eliminating, or changing the source and route of administration of IFN $\alpha$**

In view of the potential concerns regarding the use of NSAIDs in patients with COVID-19, we decided not to include Celecoxib in the current trial.

The dose of INTRON® A IFN $\alpha$  may be reduced from 20MU/m^2 to 5 MU/m^2 or to 0), in case of any observed toxicities, or in case of IFN $\alpha$  shortage.

In case of potential shortages, INTRON® A may be replaced by another form of IFN $\alpha$  at the same (Units) dose. In case the only available IFN $\alpha$  is formulated for an alternative route of administration (e.g., subcutaneous), we will adjust the dose to use the most common dose for that specific product. An IRB amendment will be submitted for any changes in formulation or dosing.

## **2.6 Overall Impact**

Our study focuses on patients with cancer, but knowledge gained about safety and immunologic correlates is expected to be applicable to other patients at high risk for COVID-19-related morbidity and mortality as well as to future viral pandemics. Using each patient's baseline nasopharyngeal viral load, we will evaluate to what extent the study regimen reduces viral load relative to supportive care only. Assessment of nasopharyngeal viral load at multiple time points will enable evaluation of early and long-term effects of the study regimen in controlling viral replication. A reduction in nasopharyngeal viral load by PCR may also reflect reduced likelihood of transmission of virus to others. As described in the Statistical Plan (Section 19), the study is non-randomized and each patient will serve as their own control regarding baseline, on-treatment, and post-treatment nasopharyngeal viral load. In addition, comparisons will be made with historical controls in which Roswell Park patients with COVID-19 were treated with standard of care and longitudinal viral load was monitored as standard of care. As described in the demonstration of safety of this regimen and reduction of nasopharyngeal viral load will establish the foundation for a larger randomized trial powered for clinical efficacy, such as reduction in respiratory failure and mortality.

Our study will enroll patients with cancer with varying comorbidities and levels of COVID-19 severity. For outpatients with COVID-19 at high risk for severe complications based on age and co-morbidities, a monoclonal antibody cocktail (e.g. Regeneron's combination of casirivimab and imdevimab) is standard of care. In patients with more severe COVID-19 who are hospitalized and require supplemental oxygen, therapy is focused on controlling inflammatory injury. Dexamethasone was associated with a survival benefit and will be administered to all patients who meet criteria for this agent. Other anti-inflammatory agents such as IL-6-targeting agents and baricitinib can also be of value, although their benefit when added to corticosteroids is unclear. The antiviral agent, remdesivir, is of unclear value based on conflicting data; at best it shortens the duration of illness but doesn't have a survival benefit. At Roswell, we routinely administer combination dexamethasone and remdesivir to inpatients with significant COVID-19, and will do so for patients enrolled in this protocol unless there is a clinical contraindication to receiving either agent. The data on convalescent plasma is also contradictory, but plasma with high neutralizing titers against the viral Spike protein is likely to be of value. We do not know the effect of these standard of care regimens on nasopharyngeal viral load in patients with cancer. In addition, since these regimens are often administered concurrently, it's difficult to delineate the effect of a specific drug on viral load. Based on our experience at Roswell Park, the nasopharyngeal viral load in some

Roswell Park Protocol No.: I-659920

immunocompromised patients with cancer (e.g. stem cell transplant recipients and patients receiving B-cell-depleting agents), has persisted for several weeks despite receiving combinations of these agents (e.g. remdesivir and dexamethasone, often in combination with convalescent plasma). The standard of care for COVID-19 changes over time. Regarding the current protocol, the study regimen will be added to what in our judgment is the best standard of care regardless of outpatient or inpatient status.

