## **4 LOCAL AND STUDY-WIDE NUMBER OF SUBJECTS**

Maximum number of Roswell Park subjects: The anticipated number of subjects required for the main portion of the study is 44. All patients must have cancer and need not be established Roswell Park patients. The modification of the protocol triggered by the observed high effectiveness of the treatment in the first patient who received rintatolimod alone will include additional 20 cancer patients (Expansion Cohort).

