## 10 TREATMENT

All patients will receive best available standard of care. Depending on the severity of COVID-19 and need for hospitalization, standard of care can include, but is not limited to, monoclonal antibody formulations directed against the SARS-CoV-2 Spike protein, remdesivir, dexamethasone, and tocilizumab. Treatment in the Main Cohort will consist of lead-in single agent rintatolimod (first 3 patients on the dose-escalation component) followed by the combination of rintatolimod and dose-escalation of rIFN $\alpha$ . Intravenous (IV) rintatolimod is administered as a fixed dose (200 mg per infusion) and IV rIFN $\alpha$  dose-escalation will be a standard 3 + 3 design, with the following doses per infusion: 0, 5, 10, and 20 MU/M $^2$ . The dose-escalation phase will lead to which patients will receive IFN $\alpha$  at 20 MU/M $^2$  or at MTD + rintatolimod (200 mg). The regimen will be administered on Day 1 and on Day 3 (or 4), and EOT assessments will occur on Day 7 ( $\pm$  1 day) and Day 14 ( $\pm$  3 days). This portion of the study will allow for additional safety data and the analysis of the effect of the study regimen on nasopharyngeal viral load. Using each patient's baseline nasopharyngeal viral load, we will evaluate to what extent the study regimen reduces viral load relative to supportive care only.

Treatment in the Expansion Cohort will be IV rintatolimod is administered as a fixed dose (200 mg per infusion on Day 1 and on Day 3 (or 4). Based on the PI's judgment, additional infusions of rintatolimod at 200 mg may be administered 3 to 4 days apart. Decisions about additional rintatolimod infusions will be based on evaluation of AEs attributed to rintatolimod, particularly increased FIO $_2$  needs. A maximum of 12 rintatolimod infusions may be administered per patient. The rationale for a maximum of 12 infusions was based on discussions with leadership from AIM Immunotech regarding the expected effects of rintatolimod on innate immune responses over time based on data from patients with and without cancer. Rintatolimod activates innate immune responses through a number of mechanisms including activation of RNase L and inducing interferon stimulated genes (ISGs). Administration of rintatolimod over a number of weeks may be required for sustained activation of innate immune responses to clear SARS-CoV-2.

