## **19 STATISTICAL PLAN**

### **19.1 Study Design/Endpoints**

This is prospective Phase I/IIa trial basket trial of i.v. rintatolimod administered with or without i.v. IFN $\alpha$  (INTRON $\circledR$  A) in two cohorts of patients: Main Cohort and Expansion Cohort. Only Main Cohort subjects will participate in the Phase I 3+3 portion of this study. The Expansion

Roswell Park Protocol No.: I-659920

Cohort will consist of rintatolimod without IFN $\alpha$ . Neither cohort is randomized. The kinetics of nasopharyngeal viral load will be assessed based on baseline values and on treatment and EOT values. In the Expansion Cohort, the kinetics of nasopharyngeal viral load will be compared with historical controls consisting of Roswell Park patients with COVID-19 of varying severity. All patients will receive best available standard of care in addition to study drug regimens.

**Phase I.** The Phase I component of the protocol consists of a 3+3 design with four dose levels of IFN $\alpha$  (0, 5 MU/M, 10 MU/M and 20 MU/M ) and fixed dose rintatolimod (200 mg per day) administered on Days 1 and 3. The sample size for the Phase I trial may range from n=3 to 24.

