### **19.3 Sample Size Justification**

The sample size was based on preliminary data gathered at Roswell Park on patients and employees. The values were similar between the two study groups. The Ct values collected at baseline for n=20 patients and employees had an average of 24.1 log2 copies with a standard deviation of 6.5. The standard deviations after baseline was approximately 4.5 as the Ct values increased. The preliminary estimate for the AUC based on our pilot data is 130 (log2 copies) x day, which is the basis for our null hypothesis. The between time point correlation was estimated to be approximately rho=0.3. Given n=10 subjects we will be able to detect and increase in the AUC to an average of 144 (log2 copies) x day (efficacy) or greater than our assumed institutional benchmark of 130 (log2 copies) x day at power=0.80 and alpha=0.05(one-sided). We simplified this calculation assuming no censoring, which will be accounted for in the final analysis and assumed a compound symmetry covariance structure with the correlation estimate described above.

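### Sections 2.6 and 10 present change from a patient's own baseline as showing an effect relative to supportive care; it cannot show that, and Section 19 contains no such analysis

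*Combined protocol and SAP*

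**What the plan says.** Section 2.6 states that "each patient will serve as their own control regarding baseline, on-treatment, and post-treatment nasopharyngeal viral load" and credits this design to Section 19. The inference drawn from it appears in Section 2.6 and again in Section 10: "Using each patient's baseline nasopharyngeal viral load, we will evaluate to what extent the study regimen reduces viral load relative to supportive care only". Section 2.6 then continues: "In addition, comparisons will be made with historical controls in which Roswell Park patients with COVID-19 were treated with standard of care". Section 10 mentions no historical control.

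Section 19.1 opens with a general statement: "The kinetics of nasopharyngeal viral load will be assessed based on baseline values and on treatment and EOT values". It then names an external comparator for one cohort: "In the Expansion Cohort, the kinetics of nasopharyngeal viral load will be compared with historical controls consisting of Roswell Park patients with COVID-19". Its Phase IIa paragraph nearly repeats the Section 10 sentence, but the comparator there is historical institutional benchmarks. Section 19.2.2 makes the primary efficacy test a one-sided test of mean Ct AUC against 130, and Section 19.3 takes the 130 from pilot data. Of that pilot it says: "The standard deviations after baseline was approximately 4.5 as the Ct values increased".

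Section 4 attributes the Expansion Cohort to the "observed high effectiveness of the treatment in the first patient who received rintatolimod alone". Section 9 reports that this patient had cleared the virus by Day 3, and also gives difficulty in accruing patients as a reason.

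**The concern.** A higher Ct means less virus. In an acute infection that most patients clear, Ct is expected to rise whether or not the drug works. A treated patient's baseline shows where that patient started, not where the patient would have been on supportive care alone. The pilot points the same way: Ct rose in patients and employees, and nothing in Section 19.3 says they had received the regimen. Standard of care adds a second source of change. Section 2.6 itself says that its effect on nasopharyngeal viral load in patients with cancer is unknown and hard to separate.

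Nasopharyngeal kinetics is a primary objective (Section 1.1) and a primary endpoint (Section 8.1). Section 2.6 also makes a reduction in viral load part of the foundation for a larger randomized trial. Followed literally, the sentences in Sections 2.6 and 10 would let a plain rise in Ct be reported as a reduction relative to supportive care.

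**Working it through.** **Which comparator each section gives**

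| Place | Comparator for viral load |
|---|---|
| 2.6 | Own baseline, described as relative to supportive care; historical controls in addition |
| 10 | Own baseline, described as relative to supportive care |
| 19.1, general | Baseline, on-treatment and end-of-treatment values only |
| 19.1, Expansion Cohort | Historical Roswell Park patients |
| 19.1 and 19.2.2, Phase IIa (n = 10) | Historical benchmark, AUC = 130 |
| Section 19, Phase I (3 to 24 patients) | None named beyond own baseline |

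Section 2.6 therefore credits Section 19 with a design for which Section 19 specifies no test. Within Section 19, Phase I kinetics have no external reference.

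**Illustration of how uninformative own-baseline change is.** The plan gives no figure for this comparison and specifies no paired test, so there is nothing to reproduce. The power of 0.80 in Section 19.3 belongs to the AUC test and is not used here.

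Inputs from Section 19.3: baseline SD 6.5, later SD about 4.5, correlation between time points about 0.3. From Section 19.1: n = 10. From Section 19.2.2: additional tests are two-sided at 0.05, and only the primary test is one-sided. The size of the natural rise is an assumption, because the documents give its direction only.

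SD of change from baseline to one later visit:

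sqrt(6.5² + 4.5² − 2 × 0.3 × 6.5 × 4.5) = sqrt(42.25 + 20.25 − 17.55) = sqrt(44.95) = 6.70 Ct

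Standard error with n = 10: 6.70 / sqrt(10) = 2.12. The noncentrality is rise / 2.12. The probability of a significant rise comes from the noncentral t with 9 degrees of freedom, assuming no drug effect and counting rejection in the upper tail:

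| Assumed natural rise (Ct) | Noncentrality | Two-sided 0.05 | One-sided 0.05 |
|---|---|---|---|
| 3 | 1.41 | 24% | 37% |
| 5 | 2.36 | 56% | 70% |
| 7 | 3.30 | 84% | 92% |
| 10 | 4.72 | 99% | >99% |

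For one full Phase I tier of six patients (5 degrees of freedom), the two-sided figures are 14%, 32%, 54% and 83%. The one-sided figures are 24%, 47%, 71% and 93%.

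**The case against.** The strongest reply is that the plan already has an external comparator. The sentence in Section 2.6 directly after the own-control statement adds historical standard-of-care patients and does not limit them to one cohort. The only formal efficacy test is against a benchmark taken from the same pilot in which Ct rose, so the natural rise is meant to be contained in the null value. Phase I has a safety primary endpoint and no efficacy test, and the kinetics sentence in Section 19.1 makes no claim about supportive care. Section 9 gives accrual difficulty as a further reason for the Expansion Cohort. The probabilities above belong to a test the plan does not contain.

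All of this stands, and it limits the point. A reader might infer that the trial's efficacy result will count natural clearance as drug effect. The documents do not support that, because the specified test is not a within-patient test. A reader might also infer that one patient's early clearance alone produced the Expansion Cohort. Section 4 names it as the trigger, but Section 9 gives two reasons.

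The reply does not remove the sentences themselves. The historical comparison in Section 2.6 is additional, so the own-control claim remains as separate evidence, and Section 10 repeats it with no historical comparator. Nor can the benchmark be assumed to correct for natural clearance as now written. Under the Section 19.2.2 formula, a flat Ct of 24.1 over 14 days gives an AUC of 24.1 × 14 = 337, far above 130. That is a separate defect and needs its own repair.

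**Conclusion.** The point holds as one of wording and inference. Sections 2.6 and 10 claim that own-baseline change measures an effect relative to supportive care. It does not, and Section 19 provides no own-control analysis to match the claim. A within-patient rise in Ct cannot be attributed to the regimen when Ct rose in the pilot and all patients receive concurrent standard of care.

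The size of the problem depends on the natural rise, which the documents do not report. Over an assumed range of 3 to 10 Ct, an inert regimen would appear to reduce viral load in 24% to 99% of two-sided paired tests with n = 10. These figures rest on the pilot SDs and correlation, normally distributed changes and no censoring at Ct 40. They show how weak the comparison is and are not error rates of the planned primary test.

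The correction is worth making because it limits what the trial may conclude, at very little cost.

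**What to change.** - **Sections 2.6 and 10:** delete the own-control statement and replace supportive care as the comparator with the historical-benchmark wording of the Phase IIa paragraph in Section 19.1.
- **Section 19.1:** state that change from a patient's own baseline is descriptive and supports no efficacy statement in any cohort.
- **Efficacy measure:** keep AUC against the historical benchmark. A new estimand based on mean change from baseline would compete with the primary endpoint and is not needed.
- **Main Cohort, including each Phase I tier:** present Ct curves beside the historical standard-of-care data where sampling days allow, as supportive description. Section 2.6 says those patients had longitudinal viral load measured, but the documents do not give the days, so matching may be incomplete.
- **Section 4:** describe the event as early clearance in one patient, without calling it effectiveness.

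The cost is protocol wording and some tabulation of historical data, with no new patients or procedures. The downside for the sponsor is that the within-patient result can no longer be presented as evidence of efficacy.
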